6.1.2. Definition of Baseline and Postbaseline Measures

The baseline value for the efficacy (except flare), health outcomes is defined as the last non-missing measurement on or prior to the date of first study baricitinib administration. For patients who participate in the Safety/PK period, this value will be recorded on or before Visit 2 (Day 1); for the other patients who started with the OLLI period, this value will be recorded on or before Visit 5 (Week 0).

The baseline value for disease flare analyses is defined as the last non-missing measurement on or prior to the date of randomization (beginning of the DBW period). This value will be recorded on or before Visit 9 (Week 12).

Baseline for the safety analyses is defined in Section 6.18. Postbaseline measurements are collected after study drug administration through Visit 17 (Week 44) or early discontinuation visit. For data collected in the electronic Clinical Outcomes Assessment (eCOA) tablet (including Patient-Reported Outcomes [PRO] and Clinician-Reported Outcomes [ClinRO]) and related to efficacy assessments, unscheduled postbaseline visits that fall within the visit windows defined by Lilly will be summarized in the by-visit analyses if there is no scheduled visit available. Refer to clinical protocol I4V-MC-JAHV(d) for detail of the visit windows. If there is more than 1 unscheduled visit within the defined visit window and no scheduled visit is available, the unscheduled visit closest to the scheduled visit date will be used. If 2 unscheduled visits of equal distance are available, then the latter of the 2 will be used.

Postbaseline measures for the safety analyses are defined as the nonmissing scheduled (planned) measurements after the date of first study drug administration for continuous measures by-visit analyses and all nonmissing measurements after the date of first study drug administration for all other analyses.

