6.3. Handling of Dropouts or Missing Data

Intercurrent events (ICH E9R1) are events which occur after the treatment initiation and make it impossible to measure a variable or influence how it should be interpreted. Examples of such events include treatment discontinuation due to death or AEs, and loss to follow-up. In this study, intercurrent events will be handled by the while-on-treatment strategy and the composite strategy approaches as primary strategies. The hypothetical strategy will also be used in supplementary analysis.

The *censoring rule*: The efficacy and health outcome data collected after permanent study drug discontinuation will be excluded from the analyses. This censoring rule will be applied to all continuous and categorical efficacy and health outcome endpoints.

For binary response variables that are derived from component scores, the following steps will be implemented unless otherwise specified: If all component scores are missing at a visit, the response status will be set to nonresponse; if at least 1 component score is nonmissing at a visit, the LOCF approach will be applied to impute the missing components within a treatment period. If the binary response status still cannot be determined after LOCF, the binary response status will be set to nonresponse. The detail of the missing data definition and imputation rule is documented in [Table JAHV.6.4](#) and [Table JAHV.6.5](#).

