
Inactive disease
	
Inactive disease is indicated by the presence of all of the following (Wallace et al. 2011):
 
 No joints with active arthritis based on JADAS-27 No fever, rash, serositis, splenomegaly, hepatomegaly, or generalized lymphadenopathy attributable to JIA as assessed by the investigator No active uveitis as assessed by the investigator Normal erythrocyte (ESR) or hsCRP (ie, within normal limits in the local laboratory or, if elevated, not attributable to JIA) Physician's Global Assessment of Disease Activity indicating no active disease (best possible score on scale [0]) Duration of morning stiffness less than 15 minutes In inactive disease analysis as secondary endpoint, ESR measure is used as acute-phase reactant measure. 	
Proportion of patients who achieved inactive disease
	
 Step 1: If joint with active arthritis isn't 0, stop; else Step 2: If there is fever, rash, serositis, splenomegaly, hepatomegaly, or generalized lymphadenopathy attributable, stop; else Step 3: If uveitis, stop; else Step 4: If ESR>20, stop; else Step 5: If physician's global assessment of disease activity isn't 0, stop; else Step 6: If stiffness >15min, stop; else Step 7: Conclude the patient achieved inactive disease status. 	
Missing if any component is missing. NRI will be applied to missing data.

Secondary Efficacy Endpoint Analyses

Measure	Description	Variable	Derivation/Comment	Imputation Approach if with Missing Components
Minimal disease activity	Minimal disease activity is calculated based on the scores from the Physician's Global Assessment of Disease Activity, Parent's Global Assessment of Patient's overall Well-Being, and the number of swollen joints as described in Consolaro et al. 2012.	Proportion of patients who achieved minimal disease activity	
 • if physician's global assessment of disease activity ≤ 3.5, and • if parent's global rating of patient's overall well-being ≤ 2.5, and • if swollen joint count ≤ 1, then conclude the patient reaches minimal disease activity; all else conclude the minimal disease activity is not reached. 	
Component is missing if baseline or postbaseline value is missing. LOCF will be applied for post baseline missing values.
 
If all components are missing after LOCF, NRI will be applied to missing data.

Secondary Efficacy Endpoint Analyses

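### Minimal disease activity depends only on values at the visit, but the SAP treats a component as missing when its pre-drug baseline is missing, so an observed success can be coded as a failure

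*SAP*

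**What the plan says.** In SAP 6.10.2, the minimal disease activity row of Table JAHV.6.4 sets three conditions on the values at a visit: physician "global assessment of disease activity ≤ 3.5", parent-rated "overall well-being ≤ 2.5", and no more than one swollen joint. The derivation closes with a catch-all: "then conclude the patient reaches minimal disease activity; all else conclude the minimal disease activity is not reached". No condition involves change from baseline.

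The imputation column of that row begins "Component is missing if baseline or postbaseline value is missing". It then confines LOCF to gaps after baseline, and ends "If all components are missing after LOCF, NRI will be applied to missing data".

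Two other places bear on this:

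- SAP 6.1.2 defines baseline for efficacy measures other than flare as the "last non-missing measurement on or prior to the date of first study baricitinib administration".
- SAP 6.3, on binary endpoints built from components, says: "If the binary response status still cannot be determined after LOCF, the binary response status will be set to nonresponse". It refers the reader to Table JAHV.6.4 and Table JAHV.6.5 for the detailed missing-data definitions.

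**The concern.** The flare and PedACR rows of Table JAHV.6.4 carry the same missing-component sentence. It belongs there, because a percentage change cannot be computed without a baseline. Minimal disease activity is a state at a visit, so the baseline is not needed. Inactive disease, the other visit-state endpoint in the table, has no baseline condition. The sentence in the minimal disease activity row looks carried over from the change-type rows.

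Applied as written, the rule discards visit values that were observed and that settle the endpoint, because of a value the endpoint never uses. The misclassification runs only one way, from success to failure. A missing pre-drug value stays missing, so the effect can recur at any open-label or double-blind visit.

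**Working it through.** The plan gives no figure for this point, so there is none to reproduce. The check has three parts: what the rule does, which component is exposed, and how large the effect can be.

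**1. What the rule does.** Take a child whose three visit values are all observed.

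| Pre-drug baselines | Meets all three cut-offs at the visit? | Rule as written | Visit values only |
|---|---|---|---|
| All present | Yes | Reached | Reached |
| All present | No | Not reached | Not reached |
| One or two missing | Yes | Not reached (catch-all, SAP 6.3) | Reached |
| One or two missing | No | Not reached | Not reached |
| All three missing | Yes | Not reached (NRI) | Reached |
| All three missing | No | Not reached | Not reached |

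The two rules differ only for a child who meets every cut-off and lacks at least one baseline. LOCF does not help, because it fills only postbaseline gaps. The row's NRI sentence covers only the case with all components missing. With one or two missing, failure comes from the catch-all clause and from SAP 6.3.

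**2. Which component is exposed.** Protocol Tables JAHV.1 and JAHV.2 schedule the joint assessment and physician global at screening and again at Visit 2 or Visit 5. Each therefore has two chances to supply a pre-drug value. Parent global is part of the CHAQ (Protocol 9.1.5), which before dosing is scheduled only at Visit 2 or Visit 5. One missed form is enough. Under the SAP's PedACR row, response cannot be assessed only when more than three components are missing. A missing baseline CHAQ removes two (parent global and physical function), so such a child can still count as a responder and be randomized.

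**3. Size.** Inputs from the documents are 64 per arm, 197 entering the open-label period (SAP 5.2) and two-sided 0.05 (SAP 6.1). Assumed, because the documents do not give them: m, the share lacking at least one component baseline, 1% to 10%; and minimal disease activity rates of 60% versus 35%, or 50% versus 30%.

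- Most one child can cost an arm at one visit: 1/64 = 1.56 points.
- Expected cost per affected child: 1.56 × the chance of qualifying at that visit. At 35% this is 0.55 points; at 60% it is 0.94.
- Affected children per arm at m = 2% to 5%: 0.02 × 64 = 1.3 to 0.05 × 64 = 3.2. Successes lost at a visit: 1.28 × 0.35 = 0.4 to 3.2 × 0.60 = 1.9.
- Affected children in the open-label period at m = 2% to 5%: 0.02 × 197 = 3.9 to 0.05 × 197 = 9.9.

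If missingness is unrelated to outcome, a true rate p becomes p(1 − m) in each arm, and the difference is multiplied by (1 − m). Power is for an unadjusted comparison of two proportions with 64 per arm.

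| m | 60% vs 35%: difference (points) | Power | 50% vs 30%: difference (points) | Power |
|---|---|---|---|---|
| 0 | 25.0 | 81.6% | 20.0 | 63.9% |
| 1% | 24.75 | 80.9% | 19.8 | 63.2% |
| 2% | 24.5 | 80.1% | 19.6 | 62.5% |
| 5% | 23.75 | 77.7% | 19.0 | 60.2% |
| 10% | 22.5 | 73.5% | 18.0 | 56.5% |

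In the single-arm open-label summary, a true 50% would be reported as 0.50 × 0.95 = 47.5% at m = 5%.

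**The case against.** The strongest reply is that a competent programmer would never produce this result. The derivation column tests visit values only. SAP 6.3 speaks of component scores being present or absent at a visit. The row itself is silent on one or two missing components. On that view the sentence is stray text.

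It is true that failure with one or two missing components has to be assembled from the row and SAP 6.3; the row's NRI sentence does not state it. But SAP 6.3 sends the reader to this table for the missing-data definition, so the sentence is an operative rule. A programmer who ignores it departs from the SAP.

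The objection on size stands. Baseline is the last non-missing pre-dose value, two of the three components have two scheduled chances, and Protocol 5.1.1 asks for all baseline assessments before the first dose. No source in the documents supports a particular value of m. The share among randomized children may also differ from the share at entry, since a child lacking parent global must reach PedACR30 on the remaining components.

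A reader might infer two stronger claims that do not hold:

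- **An affected child costs 1.6 points at all eight double-blind visits.** That needs the child to qualify at all eight. At any visit where a cut-off is missed, both rules give failure. Likewise, 4 to 10 of 197 would count children lacking a baseline, not successes lost.
- **The rule biases the comparison or adds noise to it.** The missing value predates randomization, so it is balanced between arms in expectation. The effect is proportional shrinkage.

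**Conclusion.** The point holds as a defect in a stated rule. As written, the SAP can code a child with three observed, qualifying visit values as not in minimal disease activity, because of a pre-drug value the endpoint does not use. The open-label proportion is lowered directly. The double-blind difference is diluted by about (1 − m), assuming missingness is unrelated to outcome, and neither arm is systematically favoured.

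The practical size is unknown and probably small: at most 1.6 points per affected child per arm, and only at visits where that child qualifies. Under the assumed 60% versus 35%, m = 5% would cost 1.25 points of a 25-point difference and about 4 points of power. If every child has a pre-drug value for all three components, nothing changes. Minimal disease activity is one of many secondary endpoints tested without multiplicity control (SAP 6.5). The primary analysis, sample size and futility rule do not use it. This is a wording correction worth making, not a threat to the trial's conclusions.

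**What to change.** In the minimal disease activity row of Table JAHV.6.4, make two edits to the imputation column:

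- Remove the baseline condition. Suggested text: *Component is missing if the value at the visit is missing; LOCF is applied within the treatment period.*
- Replace the NRI sentence so that it covers partly missing data. Suggested text: *If any component is still missing after LOCF and the status cannot be determined, the patient is a non-responder.* This agrees with SAP 6.3.

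The second edit is needed because the first alone leaves the row silent on one or two missing components.

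The cost is two sentences and a line of derivation code, made before lock while treatment is still blinded. A blinded count of children lacking a pre-drug value for any of the three components would show whether any result is affected. Where all baselines are present the two rules give identical results, so the change has no downside.

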All safety data will be descriptively summarized in each treatment period using corresponding populations. Comparison between baricitinib and placebo will be performed during the DBW period for the DBW population. The Fisher exact test will be used for the AEs, discontinuations, and other categorical safety data for between-treatment-group comparisons in the DBW period. Continuous vital signs, body weight, and other continuous safety variables, including laboratory variables, will be analyzed using ANCOVA with treatment and baseline value in the model in the DBW population.

Any change to the data analysis methods described in the protocol will require an amendment ONLY if it changes a principal feature of the protocol. Any other change to the data analysis

methods described in the protocol, and the justification for making the change, will be described in the clinical study report. Additional exploratory analyses of the data will be conducted as deemed appropriate. Complete details of the planned analyses will be documented in the SAP.

The SAP was approved before the first patient visit in Study JAHV.

Missing Data Imputation

The following methods for imputation of missing data will be used:

1. Nonresponder imputation (NRI): All patients who discontinue the study will be defined as nonresponders for the NRI analysis for categorical variables, such as PedACR30/50/70/90/100, from the time of discontinuation and onward.
2. Last observation carried forward (LOCF): The LOCF method will be used for the analysis of continuous endpoints (unless otherwise stated). For patients who discontinue the study, the last nonmissing observation will be carried forward to the subsequent time points for evaluation.

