6.3.2. Non-Responder Imputation (NRI)

A non-responder imputation (NRI) imputation method can be justified based on the composite strategy (ICH E9R1) for handling intercurrent events. In this strategy a patient is defined as a responder only if (i) they meet the clinical requirements for response at the predefined time and (ii) they remain on the assigned study treatment. Failing either criteria by definition makes them a non-responder.

Binary efficacy and health outcome variables will be imputed using NRI after applying the censoring rule to those who discontinued study drug. Patients will be considered a non-responder for the NRI analysis if they do not meet the clinical response criteria or are entirely missing the visit at the analysis time point. Randomized patients without at least 1 postbaseline observation will also be defined as non-responders for the NRI analysis.

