		Proportion of patients with disease flare	The detail of disease flare calculation is documented in separate disease flare and PedACR response calculation algorithm document.	
The details of handling of missing data are documented in separate disease flare and PedACR response calculation algorithm document.

Secondary Efficacy Endpoint Analyses

Measure	Description	Variable	Derivation/Comment	Imputation Approach if with Missing Components
PedACR response	
Pediatric American College of Rheumatology (PedACR x%) responder is defined as patients who demonstrate disease response improvement of $\geq x\%$ in at least 3 of 6 Pediatric American College of Rheumatology (PedACR) core response variables and $>30\%$ worsening in not more than 1 of the remaining variables. (PedACR30; Giannini et al. 1997). When PedACR response is analyzed as secondary endpoint, ESR measure is used as acute-phase reactant in the core criteria.
	
PedACR 30/50/70/90/100 response rates (compare to patient's condition prior to first dose of investigational product)
	
The detail of disease flare calculation is documented in separate disease flare and PedACR response calculation algorithm document.
	
Component is missing if baseline or postbaseline value is missing. LOCF will be applied for post baseline missing values. If more than 3 components are missing, there will not be sufficient information; thus, the patient will be considered as a non-responder.
 
The detail of handling of missing data is documented in separate disease flare and PedACR response calculation algorithm document.

Secondary Efficacy Endpoint Analyses

Measure	Description	Variable	Derivation/Comment	Imputation Approach if with Missing Components
Active joint count	Number of active joints (defined as a joint that is swollen or in the absence of swelling has loss of passive motion accompanied by either pain on motion or joint tenderness) in 73 joints.	Change from baseline of active joint count	Calculation: Change from baseline: observed active joint count at visit minus baseline active joint count	Missing if baseline or postbaseline value is missing. LOCF will be applied for post baseline missing values.

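### The SAP's imputation cell for minimal disease activity conflicts with SAP 6.3, SAP 6.3.2 and the protocol, leaving open whether children who exit the withdrawal period can still count as successes

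*SAP*

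**What the plan says.** **The MDA cell.** In SAP Table JAHV.6.4 (section 6.10.2) MDA requires three things: physician global at most 3.5, parent global at most 2.5, and "swollen joint count ≤ 1". The imputation cell calls a component missing if its baseline or postbaseline value is missing. It then states "LOCF will be applied for post baseline missing values" and ends "If all components are missing after LOCF, NRI will be applied to missing data".

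**The general SAP rules.** Section 6.3 says "If all component scores are missing at a visit, the response status will be set to nonresponse", and that "if at least 1 component score is nonmissing at a visit, the LOCF approach will be applied to impute the missing components". It applies only where nothing else is specified, and it refers to Tables JAHV.6.4 and JAHV.6.5 for the detail. Section 6.3.2 requires a responder to remain on assigned treatment. It also makes nonresponders of patients who "are entirely missing the visit at the analysis time point", with no exception clause.

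**The protocol.** Section 10.3.1 says "All patients who discontinue the study will be defined as nonresponders for the NRI analysis for categorical variables", from discontinuation onward. Table JAHV.8 lists DBW MDA as logistic regression with nonresponder imputation (NRI). Sections 5.1 and 5.4 have flaring patients discontinue the study, so the protocol's NRI rule covers them.

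**The concern.** The cell places last-observation-carried-forward (LOCF) before NRI and does not limit LOCF to visits where something was observed. If it is programmed as written, a child with one DBW value has no missing component at any later visit. NRI then never reaches that child, and the last MDA status stands to Week 44.

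This can include flare exits. Flare is judged by relative worsening from Week 12 on six criteria, while MDA is an absolute state on three measures, so one visit can satisfy both. More flares are planned on placebo than on baricitinib, so carrying flare-visit successes forward raises the placebo rate more and shrinks the contrast. Dropouts carried as successes raise both arms, and would bias the comparison if dropout were unequal.

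Two analysts who start from different SAP sections could therefore report different results for one endpoint.

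The baseline condition is a second, smaller fault. MDA compares current values with fixed limits and uses no baseline.

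**Working it through.** **1. Planning inputs** (protocol 10.1 and SAP 5.2): 64 per arm, flare 35% v 60%, dropout no greater than 10%, two-sided 0.05. The plan gives no figure for MDA. The inputs do reproduce the primary-endpoint power:

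- Hazard ratio = ln(0.65)/ln(0.40) = 0.470.
- With 10% of 128 lost, events = 115.2 × 0.475 = 54.7.
- Schoenfeld power is 79.7%, against about 80% stated.

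**2. Children whose status depends on the rule.** Exits = 64 × (flare + dropout).

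- Baricitinib: 64 × 0.45 = 28.8.
- Placebo: 64 × 0.70 = 44.8.

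These are upper counts. A flare recorded at Week 44 itself has observed values. A child with no DBW value cannot be carried, because SAP 6.3.1 bars LOCF across the two periods.

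**3. Can a flare visit meet MDA?** A constructed record, with at most 1 swollen joint at Week 16:

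| | Active joints | Limited joints | Physician (0–10) | Parent (mm) | CHAQ | ESR |
|---|---|---|---|---|---|---|
| Week 12 | 1 | 1 | 0.5 | 5 | 0.25 | 15 |
| Week 16 | 3 | 3 | 2.5 | 25 | 0.375 | 15 |
| Worsening | 200% | 200% | 400% | 400% | 50% | 0% |

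Five criteria worsen by at least 30%. Both joint counts rise by 2, and both globals rise by 20 mm or its equivalent, so this is a flare. The same visit meets MDA: physician 2.5 ≤ 3.5, parent 2.5 ≤ 2.5 on the 0–10 scale, and swollen joints at most 1. Under the literal cell this child is in MDA at Weeks 20 to 44. Under SAP 6.3.2 and the protocol the child is a nonresponder.

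**4. Effect on the Week 44 proportions.** Let m be the MDA rate among stayers, and assume dropouts had the same rate at their last visit. Let s be the share of flare exits meeting MDA at the flare visit. Neither m nor s is in the documents.

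- NRI = (1 − flare − dropout) × m.
- Literal cell = NRI + flare × s + dropout × m.

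With m = 0.60:

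- NRI: 0.55 × 0.60 = 33.0% v 0.30 × 0.60 = 18.0%, a difference of 15.0 points.
- Carried dropouts add 0.10 × 0.60 = 6.0 points to each arm.

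| s | Baricitinib | Placebo | Difference (points) |
|---|---|---|---|
| 0% | 39.0% | 24.0% | 15.0 |
| 10% | 42.5% | 30.0% | 12.5 |
| 25% | 47.75% | 39.0% | 8.75 |
| 50% | 56.5% | 54.0% | 2.5 |

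In general the literal difference is 0.25 × (m − s), against 0.25 × m under NRI. With m = 0.80 that is 20.0 points under NRI, and 20.0, 17.5, 13.75 or 7.5 points under the literal cell for the same four values of s.

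**The case against.** The best defence is that the SAP already handles exits. Section 6.3.2 makes a child who is off treatment or absent from the visit a nonresponder, without exception. The column heading concerns missing components rather than missing visits. Section 6.3 confines component LOCF to a treatment period, and section 6.1.3 ends that period at flare or early discontinuation. The JADAS-27 row adds an explicit step for carrying the whole score, and the MDA row has none.

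Much of this stands, and it rules out the stronger reading. A reader might infer that the cell deliberately replaces NRI, because its final condition could never arise under section 6.3. That does not follow. The cell itself counts a component as missing when its baseline is missing, so a child observed at the visit but without baselines would trigger the condition.

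The defence does not remove the conflict, for three reasons:

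- Section 6.3 defers to the table, and nothing says section 6.3.2 outranks it.
- The cell mentions NRI only as a last step after LOCF, whereas the inactive-disease row goes straight to NRI.
- Section 6.3.1, written for continuous endpoints, treats flare as a way of completing the DBW and endorses LOCF beyond it. An analyst could borrow that reasoning.

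A reader might also extend the point to PedACR, whose row says "If more than 3 components are missing, there will not be sufficient information; thus, the patient will be considered as a non-responder" after LOCF. The documents do not support that as a finding, because the row leaves its missing-data detail to a separate algorithm document that is not available here.

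Finally, the constructed record sits on several boundaries. It shows that a flare exit can meet MDA, not how often.

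**Conclusion.** The point holds as an unresolved conflict within the SAP, and between one SAP cell and the protocol. It is not a settled change of endpoint rule. Under the literal cell, up to about 29 of 64 baricitinib and 45 of 64 placebo children could have their Week 44 MDA status set by carry-forward instead of nonresponse.

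With m = 0.60, equal dropout of 10% and dropouts at the stayer rate, the planned contrast of 15.0 points either stays the same with both arms 6 points higher (s = 0%) or shrinks to as little as 2.5 points (s = 50%). The direction under these assumptions follows from the planned flare rates whenever s is above zero. The size depends on m and s, which are assumed.

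Only a secondary endpoint without multiplicity control (SAP 6.5) is affected. The primary time-to-flare analysis and the 128 randomized are not. The conflict should be corrected because the endpoint currently has two definitions.

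**What to change.** Replace the MDA imputation cell in SAP Table JAHV.6.4 with:

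> LOCF within the treatment period imputes a missing component only at a visit where at least 1 of the 3 components was observed on treatment. If all 3 are missing at the visit, or the patient has left the DBW period (flare or discontinuation), the patient is not in minimal disease activity (NRI). No baseline value is required.

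If a carry-forward result is wanted, label it supplementary. For PedACR, only confirm that the separate algorithm document applies the rule in SAP 6.3 and 6.3.2.

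The cost is one table cell and the matching program line before unblinding, with no new data. The downside is that reported MDA percentages may be lower in both arms than under carry-forward.
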